Hybrid Ablation Plus Medical Therapy for Persistent Atrial Fibrillation
(HYBRID-AF)

ClinicalTrials.gov ID: **NCT04190186**

March 03, 2025

Statistical Analysis Plan for the HYBRID-AF Trial

1. Introduction This Statistical Analysis Plan (SAP) outlines the planned statistical analyses for the HYBRID-AF Trial, which has concluded.

2. Study Objectives The HYBRID-AF Trial evaluates the effectiveness of Biotronik ICM-guided intervention in reducing atrial fibrillation (AF) burden in patients with symptomatic persistent AF post-ablation. The primary objective is to compare AF burden between months 3 and 15 post-ablation between the Biotronik ICM-guided arm and the conventional AF management arm.

3. Study Design

- Randomized, controlled trial with 90 subjects assigned 1:1 to either conventional AF management or Biotronik ICM-guided management.
- Follow-up assessments at 3, 6, 9, 12, and 15 months post-randomization.
- Primary and secondary endpoints will be analyzed according to the intent-to-treat (ITT) principle.

4. Endpoints

Primary Endpoint:

- AF burden, defined as the percentage of time a subject experiences AF between months 3 and 15 post-ablation, measured by the Biotronik ICM.

Secondary Endpoints:

1. Composite endpoint of:
 - Clinically significant (>30 min) atrial arrhythmia (AF, atrial flutter, or atrial tachycardia) detected by Biotronik ICM post-index ablation.
 - Symptomatic AF recurrence (any duration).
 - Repeat AF ablation.
 - Cardiac hospitalization.
 - Death.
 - Healthcare utilization (hospitalization, ED visits, unplanned office visits).
2. Incidence of atrial flutter or tachycardia post-ablation.
3. Incidence of repeat procedures.
4. Major adverse events requiring rehospitalization.
5. Quality of life (QOL) assessment.

5. Sample Size Justification Based on prior studies and preliminary data, AF burden is expected to be 25% in the conventional group and 16% in the intervention group, with a standard deviation of 15%. A Wilcoxon rank-sum test at a two-sided alpha level of 0.05 and 80% power determined that 90 subjects (with a 10% dropout rate) were required.

6. Statistical Methods

Primary Analysis:

- AF burden comparison between groups using the Wilcoxon rank-sum test.
- Descriptive statistics for median and interquartile range (IQR) of AF burden.
- Sensitivity analysis for missing data using multiple imputation.

Secondary Analyses:

- Kaplan-Meier survival analysis for time to first atrial arrhythmia event.
- Cox proportional hazards regression for risk factors associated with AF recurrence.
- Poisson regression for healthcare utilization.
- Mixed-effects models for QOL changes over time.

Subgroup Analyses:

- Stratification by baseline AF burden, age, and sex.
- Sensitivity analysis excluding early dropout subjects.

7. Data Handling

- All analyses will follow an ITT approach.
- Missing data will be addressed using multiple imputation and sensitivity analyses.
- Data management will be conducted per Good Clinical Practice (GCP) guidelines.

8. Reporting and Interpretation

- All results will be reported with 95% confidence intervals and p-values.
- Statistical significance is defined as $p < 0.05$.
- Study findings will be presented in accordance with CONSORT guidelines.

9. Conclusion This SAP ensures rigorous and transparent statistical analyses for the HYBRID-AF Trial, aligning with ClinicalTrials.gov reporting requirements.

Hybrid Ablation Plus Medical Therapy for Persistent Atrial Fibrillation

Lead Principal Investigator: [name]

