17. DATA ANALYSIS PLAN

For the primary endpoint of AF burden, i.e. percentage of overall follow-up spent by the subject experiencing atrial arrhythmias, the Wilcoxon rank-sum test will be used to statistically compare the conventional group vs. the active treatment group.

For the secondary composite end point, we will perform longitudinal event-free survival analysis, defined by survival and freedom from atrial arrhythmias, re-ablation, and cardiac hospitalization. Event-free survival rates, as captured by the composite secondary endpoint, will be displayed using the method of Kaplan-Meier. We will use the log-rank test to non-parametrically compare the overall survival curves for the two treatments. The other secondary endpoints of atrial flutter/tachycardia recurrence, repeat ablation incidence, and major adverse events will be compared utilizing negative binomial regression tests to statistically compare the event rates in the two arms, using the natural log of follow-up time as an offset. Quality of life measures will be compared between the arms using the non-parametric Wilcoxon rank-sum test.

The estimate for the sample size necessary to compare AF burden at 12 months between the conventional AF management arm vs. the Bio-Monitor 3-guided repeat ablation arm will assume a 1:1 distribution of subjects between the two arms. Since most of the re-ablation procedures will be carried out based on ICM-detected subclinical AF recurrences, we conservatively expect a re-ablation rate of 50% in the intervention arm vs. 5% in the conventional arm (in which only clinical episodes will be treated and resumption of antiarrhythmic medical therapy is also allowed).

For the planned analysis of the primary end point of AF burden involving the Wilcoxon rank-sum test, a two-sided $\alpha = 0.05$ and power of 80% was assumed. Based on our preliminary data and our prior studies on AF burden (The HARMONY Trial, Circulation Arrhythmia and Electrophysiology, 2015), the 12 month primary outcome of AF burden is assumed to be 25% vs. 16% in the conventional group, with a standard deviation of 15% (a conservative estimate which allows for 10% drop-out). A reduction from 25% to 16% and 80% power,

with a drop-out rate of 10%, will result in a total sample of 90 patients.

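### The SAP describes a concluded trial, calls its analyses planned, and departs from protocol Section 17 on the secondary endpoints without listing or explaining the changes

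*Combined protocol and SAP*

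**What the plan says.** The SAP is in the same file as the protocol, under a cover date of 3 March 2025. Section 1 of the SAP states that it "outlines the planned statistical analyses for the HYBRID-AF Trial, which has concluded".

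Protocol Section 17 had already set the secondary analyses:

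- **Composite (endpoint 1):** event-free survival shown by Kaplan-Meier, with a between-arm test: "We will use the log-rank test to non-parametrically compare the overall survival curves for the two treatments".
- **Flutter or tachycardia, repeat procedures, major adverse events (endpoints 2-4):** to be "compared utilizing negative binomial regression tests to statistically compare the event rates in the two arms", with log follow-up time as offset.
- **QOL (endpoint 5):** "Quality of life measures will be compared between the arms using the non-parametric Wilcoxon rank-sum test".

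SAP Section 6 gives a different list. Kaplan-Meier is applied to time to first atrial arrhythmia. The other secondary entries are "Cox proportional hazards regression for risk factors associated with AF recurrence", Poisson regression for healthcare utilization, and "Mixed-effects models for QOL changes over time". Subgroups by baseline AF burden, age and sex follow, with an analysis that leaves out early dropouts. SAP Section 8 adds: "All results will be reported with 95% confidence intervals and p-values". It sets significance at p below 0.05 and distinguishes no class of analysis.

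**The concern.** Pre-specification lets a reader take a nominal p-value at face value. A SAP that describes a finished trial, and departs from the protocol without saying so, weakens that assurance for every analysis it changed or added.

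Two consequences matter in practice. First, an analyst who follows the SAP alone will not produce the between-arm tests that the protocol promised for the composite and for endpoints 2-4. Second, a late-added analysis with p below 0.05 can be reported as planned, when the documents cannot show that it was planned before results by arm could be seen.

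The documents do not exclude such access. They describe no blinding of the study team or analysts. The study team supplied monthly monitor reports in the intervention arm (protocol Section 4), monitor data were collected monthly in both arms (Section 8), and one centre handled coordination, database management and statistical analysis (Section 15).

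**Working it through.** The plan gives no figure of its own on this point, so the check is mainly a comparison of protocol Section 17 with SAP Section 6.

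| Item | Protocol Section 17 | SAP Section 6 | Nature of difference |
|---|---|---|---|
| Primary, AF burden | Wilcoxon rank-sum | Wilcoxon rank-sum | Test unchanged |
| Endpoint 1, composite | Kaplan-Meier and log-rank on event-free survival | Kaplan-Meier for first atrial arrhythmia, no between-arm test named | Outcome replaced, test omitted |
| Endpoints 2-4 | Negative binomial, log follow-up offset | No method named | Omitted |
| Endpoint 5, QOL | Wilcoxon rank-sum | Mixed-effects models | Replaced |
| Risk factors for recurrence | None | Cox regression | Added |
| Healthcare utilization on its own | None | Poisson regression | Added |
| Subgroups | None | Baseline AF burden, age, sex | Added |
| Early-dropout exclusion | None | Sensitivity analysis | Added, but see below |

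Two rows need a note.

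- **QOL.** Protocol Sections 4 and 8 and Table 1 place the questionnaire at baseline and 15 months only. A mixed model can be fitted to two occasions, so the method is not invalid. There is only one change to estimate, however, and the SAP gives no reason for leaving the rank-sum test.
- **Early dropout.** Protocol Section 13 already removes patients with under 3 months of follow-up from the primary analysis. The SAP does not define early dropout, so it is unclear whether its analysis is that exclusion or a new one.

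**Size, as an illustration.** Suppose that one endpoint has two candidate analyses and that the one with the smaller p-value is reported. With no true effect, let the test statistics Z1 and Z2 be standard normal with correlation ρ. The error rate is

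P( max(|Z1|, |Z2|) > 1.96 ).

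It was simulated with 1,000,000 draws of Zj = √ρ·A + √(1−ρ)·Ej, where A, E1 and E2 are independent standard normals:

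| Assumed ρ | Error rate |
|---|---|
| 0.95 | 6.4% |
| 0.9 | 7.0% |
| 0.7 | 8.3% |
| 0.5 | 9.1% |

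At ρ = 1 the rate is 5%. At ρ = 0 it is 1 − 0.95² = 1 − 0.9025 = 9.75%.

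The correlations are assumptions; the documents give none. The illustration applies to QOL, which has two named analyses. It applies to the time-to-event endpoint only if a between-arm test were attached to the SAP's arrhythmia curve. It cannot apply to endpoints 2-4, where no second analysis is named.

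**The case against.** The strongest reply has five parts.

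- **The SAP is open about its timing.** Section 1 says that the trial is over, and Section 17 is in the same file, so anyone can identify the changes. This stands. It would be wrong to say that pre-specified and later analyses cannot be told apart. What remains unknown is when and why each change was made.
- **A concluded trial is not the same as unblinded data.** No lock date or record of access to results by arm is given. This also stands. A reader might infer that methods were chosen because of the results, but the documents do not support that. They are silent either way.
- **Silence is not change.** A reader might say that all five secondary analyses were altered. For endpoints 2-4 the SAP names no method and does not say that Section 17 is superseded, so these are omissions. The Cox model is for risk factors and is not described as an arm comparison. Poisson covers an outcome for which Section 17 had no stand-alone method. The clear replacements are QOL and the composite.
- **An error rate near 10% is a bound.** It needs two independent tests, and two analyses of the same endpoint in the same patients are normally correlated.
- **Section 17 has no hierarchy or multiplicity rule either.** Its secondary tests were pre-specified, but their joint error was never controlled. Restoring them does not change that.

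The SAP could also be read as a supplement to the protocol. It does not say so. On that reading QOL and the time-to-event endpoint each have two analyses, with no rule for which governs.

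**Conclusion.** The point holds for the secondary and subgroup analyses. The SAP replaces the analysis of two secondary endpoints (composite and QOL), leaves three (2-4) without their pre-specified comparison, and adds further analyses. It does this under the label of planned work and a single 0.05 threshold, with no change list, reason or statement of data access.

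The primary rank-sum test is the same in both texts, so its choice is not in doubt on this ground.

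If selection between two analyses were possible, a nominal 5% error would become roughly 6-9% under correlations of 0.95 to 0.5. The conclusion does not depend on that range. It rests on the SAP's own statement that the trial was over and on the comparison with Section 17. It makes no claim that any choice was driven by results.

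**What to change.** 1. Run and report the Section 17 analyses as the pre-specified secondary results: log-rank on the composite, negative binomial regression with log follow-up offset for endpoints 2-4, and the Wilcoxon test for QOL. State which components the log-rank analysis counts, because Section 17 describes a shorter list than the endpoint in protocol Section 4, which also names symptomatic recurrence and healthcare utilization.
2. Add to the SAP a dated list of every departure from Section 17, with the reason and the state of access to data by arm at that date, including database lock.
3. Label SAP-only secondary and subgroup analyses post hoc and exploratory, without significance claims. Exempt any for which the sponsor can document that the choice preceded access to data by arm.
4. Keep the multiple-imputation analysis of the primary endpoint as a sensitivity analysis. Define early dropout. If it means the Section 13 exclusion, say so and cite that section.

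This takes SAP wording and analyses that the protocol already promised, with no new data. The downside is that some secondary results become exploratory.

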5. INCLUSION AND EXCLUSION CRITERIA

Inclusion criteria

- 18 years of age or older
- History of persistent atrial fibrillation (sustained AF episode lasting more than 7 days, but less than a year)
- Planned to undergo **first** AF ablation with successful Biotronik ICM implant before or at time of ablation

Exclusion criteria

- Paroxysmal atrial fibrillation
- Long persistent atrial fibrillation (continuous atrial fibrillation that lasts more than 1 year)
- Permanent atrial fibrillation
- Left atrial diameter of 60 mm or greater
- Patients with CHF status prohibiting EP study and ablation, but may be re-considered for enrollment later after effective treatment
- Patients with metabolic derangements (e.g. renal/hepatic failure, electrolyte disturbance, etc.), prohibiting EP study and ablation or antiarrhythmic medical therapy (e.g. dofetilide, sotalol or amiodarone, etc.)
- Patients with an intra-cardiac thrombus, but may be re-considered for enrollment later after effective treatment
- Serious known concomitant disease with a life expectancy of < 1 year
- Pregnancy or nursing
- Unwilling or unable to give informed consent
- Existing CIED such as pacemaker or ICD

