8. STUDY PROCEDURES

After signing the informed consent and undergoing ICM implant prior to or at time of the AF ablation as part of standard of care, subjects will undergo randomization and the following procedures:

12 lead ECG performed as standard of care.

- Quality of life (QOL) questionnaire will be completed by the patients as part of the research study on a paper form and entered into an electronic database by the research coordinator. The questionnaire should take the patient approximately ten minutes to complete.
- Chart Review: Data regarding clinical history, medications, ablation procedure, device implantation, and follow-up data will be collected from electronic medical records prior to in-clinic or follow up calls with the patients.
- In-Clinic Visits: Per standard of care, patients will attend scheduled follow up visits at 3, 9, and 15 months. The study team will perform a medical assessment, and ask questions about adverse events.

- Follow-Up Phone Calls: Patients will receive follow-up calls from the study team at 6 and 12 months. The study team will ask questions about medication changes and any unexpected medical (adverse) events as part of research.

Method of Assigning Subjects to Treatment

Subjects will be randomized 1:1 to conventional AF management vs. ICM-guided AF management following ablation for persistent AF. Randomization will occur electronically using the electronic data collection system, TrialMaster that is available 24/7 to all study personnel.

Follow-up Schedule (See also Figure 1 and Table 1)

Following enrollment and randomization to an intervention arm ICM-based AF management vs. conventional AF management, all subjects will have scheduled follow-up visits (clinic or phone) by the study team at quarterly intervals following randomization. ICM data will be collected electronically at monthly intervals.

All subjects will be followed for a time-period of 15 months.

The following data will be collected at these time-points:

Randomization/Baseline: Baseline clinical characteristics, existing echocardiographic measures, labs, QOL questionnaire, and NYHA class will be recorded.

- *Monthly:*
 - Conventional and Interventional arm
 - Obtain ICM data remotely
- *3-months ±14 days from randomization:*
 - Conventional
 - Office visit for clinical assessment
 - Clinical and adverse events
 - Discontinue AAD after 3 months following the AF ablation procedure per treating physician discretion
 - Interventional arm

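### The primary AF-burden test is valid but uses no baseline information, so it may give up a few points of power that a two-covariate rank analysis could recover

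*Combined protocol and SAP*

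**What the plan says.** The SAP (section 6, Primary Analysis) gives the primary method as "AF burden comparison between groups using the Wilcoxon rank-sum test". Protocol section 17 agrees: "the Wilcoxon rank-sum test will be used to statistically compare the conventional group vs. the active treatment group". Neither names a covariate, a stratified rank test or an adjusted sensitivity analysis for AF burden. The planned sensitivity analyses concern missing data and early dropout. Baseline factors enter only as subgroups (baseline AF burden, age, sex) and in a Cox model for AF recurrence.

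Randomisation (protocol section 8) is electronic and 1:1, with no stratification factor stated. Four sites enrol.

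On baseline data, protocol section 8 states: "Baseline clinical characteristics, existing echocardiographic measures, labs, QOL questionnaire, and NYHA class will be recorded". One exclusion criterion in section 5 is "Left atrial diameter of 60 mm or greater", so the diameter has to be known to apply it. Table 1 ticks cardiovascular medication in the combined screening, consent and randomisation column.

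**The concern.** In a trial of 90 subjects, a baseline variable that predicts AF burden can buy power without a single extra patient. The documents themselves suggest that such variables exist. Protocol section 2 links referral without an AAD to higher recurrence, and the SAP plans a search for risk factors for recurrence. AAD status also determines which escalation step applies in the intervention arm. Yet the primary comparison uses none of this, and the randomisation is not stated to balance it. At stake is a modest amount of power in a trial that has little to spare once dropout occurs.

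**Working it through.** **Inputs.** From SAP sections 3 and 5:
- "AF burden is expected to be 25% in the conventional group and 16% in the intervention group, with a standard deviation of 15" per cent, so a difference of 9 points.
- "A Wilcoxon rank-sum test at a two-sided alpha level of 0.05 and 80% power determined" the sample size.
- "90 subjects assigned 1:1", that is 45 per arm.
- "90 subjects (with a 10% dropout rate) were required", which leaves 90 × 0.9 = 81 evaluable.

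The share of variance in AF burden explained by the covariates (R²) is not in the documents. I assume 0 to 0.20.

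**The plan's own figure.** For two means, n per arm = 2 × [15 × (1.960 + 0.842) / 9]² = 43.6, so 44 per arm and 88 in all. The Wilcoxon test has asymptotic efficiency 3/π = 0.955 for normal data: 43.6 / 0.955 = 45.7, so 46 per arm and 92 in all. The stated 90 fits these as evaluable subjects. With 10% dropout added, 92 / 0.9 gives 103. The dropout allowance is a separate matter; here it only fixes the starting power.

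**Unadjusted power.** Power = Φ(9 / [15 × √(2 / (0.955n))] − 1.960).
- n = 45 per arm: 9 / 3.236 = 2.781, less 1.960 = 0.821, power 79.4%.
- n = 40.5 per arm: 9 / 3.411 = 2.638, less 1.960 = 0.678, power 75.1%.

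Simulation with 41 and 40 subjects gives about 74%.

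**Adjusted power, two covariates, 81 evaluable.** The residual SD is 15 × √(1 − R²). Estimating two covariate effects costs roughly a factor (81 − 2 − 2 − 1) / (81 − 3) = 76/78 = 0.974 in effective sample size. At R² = 0.10 the SD is 14.23 and the effective n is 40.5 × 0.955 × 0.974 = 37.7. Then 9 / [14.23 × √(2 / 37.7)] = 2.745, less 1.960 = 0.785, power 78.4%.

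| R² (assumed) | Residual SD | Formula | Simulated rank ANCOVA | Change from Wilcoxon in points, two covariates | Change with three site indicators added |
|---|---|---|---|---|---|
| 0 | 15.00 | 74.0% | 73% | about −1 | about −3 |
| 0.05 | 14.62 | 76.2% | 74% | about 0 | – |
| 0.10 | 14.23 | 78.4% | 78% | about +3.5 | about +2 |
| 0.15 | 13.83 | 80.6% | 79% | about +5.5 | about +4 |
| 0.20 | 13.42 | 82.9% | 81% | about +8 | about +6 |

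The changes compare both tests on the same simulated trials. The Wilcoxon figure moves between about 73% and 75% from row to row through simulation error. Repeating the simulation with fresh random numbers moved no adjusted two-covariate figure by more than a point. Type I error was about 5%.

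**Break-even.** Adjustment pays once R² exceeds the cost of estimating the covariate effects: 1 − 76/78 = 0.026 for two covariates, and 1 − 73/78 = 0.064 with three site indicators as well.

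**All 90 evaluable.** Wilcoxon 78 to 79%; two covariates about 81%, 84% and 85% at R² of 0.10, 0.15 and 0.20.

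**Skewed data.** With beta-distributed burden of the same means and SD, and a five-term model including site, Wilcoxon against adjusted power was 86.5% against 84.5% (R² 0), 87.0% against 88.2% (0.10) and 87.5% against 91.0% (0.20). The pattern is the same, with smaller gains.

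**Chance imbalance.** If half the subjects use an AAD (assumed), the two arms of 45 differ by 7 or more users (15 points) in 17% of trials. If AAD use alone explained 5 to 10% of variance, users and non-users would differ by 2 × 15 × √0.05 = 6.7 to 2 × 15 × √0.10 = 9.5 points. An imbalance of 7/45 would then move the arm difference by 1.0 to 1.5 points.

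**The case against.** A plain Wilcoxon test is valid under 1:1 randomisation, and it is the test on which the sample size was based. A reader might infer that chance imbalance biases the primary result. It does not: imbalance is part of the random error that the test's 5% level already covers. Adjustment only reduces that error.

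A reader might also infer that the trial certainly loses power. The documents do not show this, because they give no figure for how strongly left atrial diameter or AAD use predicts AF burden. Below an R² of about 0.03 the two-covariate model gains nothing.

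Nor is the data cost certain to be nil. Echocardiographic data are limited to existing measures, and left atrial diameter is not a named data item. Meeting the 60 mm limit does not guarantee a recorded value. AAD use is a proper covariate only if fixed before allocation. Subjects are randomised after ablation and implant (section 4.1), the table has one combined baseline column, and later AAD use is part of the strategies being compared.

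Finally, the SAP is dated March 2025 and describes a concluded trial, so replacing the primary test could look like a choice made after seeing results.

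All of this stands. It limits the claim and the remedy, but it does not remove the case for one pre-specified adjusted analysis.

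**Conclusion.** This is a missed opportunity for precision, not an error. With 81 evaluable subjects and normal data, adjusting for left atrial diameter and prior AAD use changes power by about −1 point if the two carry no prognostic information, and by about +3.5 to +8 points if they explain 10 to 20% of variance. The omission itself is certain, since both documents agree. The size of the gain is not, because it rests on an assumed R² and smaller gains are plausible for skewed data. Site does not belong in the main adjusted model: if it is not prognostic, its three indicators cost 1 to 2 points.

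**What to change.** In SAP section 6, specify a rank ANCOVA: rank AF burden across both arms, regress the ranks on left atrial diameter (continuous) and AAD use recorded before randomisation (yes/no), and test the arm difference in the residual ranks. Leave site out. Fill missing covariate values by a simple rule that ignores arm, such as the overall median or most frequent category.

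State whether AF burden by arm had been seen when this was decided. If not, make the rank ANCOVA primary and the plain Wilcoxon supportive. If it had been seen, keep the Wilcoxon primary and report the rank ANCOVA as the first sensitivity analysis. Keep the planned medians and interquartile ranges either way.

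The cost is a few sentences and lines of code, plus a check that left atrial diameter is in the database and that the recorded AAD status predates allocation. The downside is about 1 point of power if neither covariate is prognostic.
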